8.2.2 Analysis Sets

Table 3 provides the definitions of the Analysis Sets and their purposes.

[figure not shown]
The analysis sets for PA will be drawn from all subjects randomized as of November 28, 2018 (n = 469), see Sections 6.2 and 7. Subjects not randomized (screen failure) will be included in PA analysis set if their screening date is on or before November 28, 2018. For the LTE analysis, the analysis sets will be drawn from all subjects who enter the LTE.

For analysis on HDA subpopulation, all subjects with SLEDAI-2K ≥ 10 at Screening will be included. The corresponding analysis sets will be drawn as specified above depending on the analysis (PA, LTE analysis).

Table 3: Analysis Sets

Analysis Set	Definition	Purpose
Enrolled	The Enrolled analysis set will include all subjects who sign the informed consent form.	The purpose of this analysis set is to count how many subjects signed the informed consent

ITT (Intent-To-Treat) Analysis Set	The ITT analysis set will include all randomized subjects. Subjects will be analyzed according to randomization treatment.	The ITT will be used for demographic/baseline characteristics.
mITT (modified Intent-To-Treat) Analysis Set	The mITT analysis set will include all randomized subjects who have received at least one dose of IMP (evobrutinib or placebo) and have at least one Baseline and one post-Baseline disease assessment (among the following: SFI, SLEDAI-2K, PGA, BILAG 2004, CLASI). Subjects will be analyzed according to randomized treatment. Subjects with Protocol Deviation (PD) code equal to PDEV80 are excluded from mITT.	The mITT will be used for all efficacy endpoints. The mITT will be used for demographic/baseline characteristics in case more than 10% of ITT are excluded from mITT.
Safety Analysis Set (SAF)	The Safety analysis set will include all subjects who have received at least one dose of IMP (evobrutinib or placebo). Subjects will be analyzed according to the actual treatment they receive.	The SAF will be used for the analysis of medications, exposure/compliance and safety endpoints.

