9.2 Presentation of Tables/Listings/Figures (TLFs)

Tables and figures will be sorted by treatment group (in the order stated in Table 6) and chronological time point (where applicable).

Table 6: Treatment Groups and Regimens

Treatment Group	Regimen	Presentation for the PA	Presentation for the LTE analysis (*)
1	Placebo	Placebo	Placebo/Evobrutinib 50 mg BID
2	Evobrutinib 25 mg QD (once daily)	Evobrutinib 25 mg QD	Evobrutinib 25 mg QD/Evobrutinib 50 mg BID
3	Evobrutinib 75 mg QD	Evobrutinib 75 mg QD	Evobrutinib 75 mg QD/Evobrutinib 50 mg BID
4	Evobrutinib 50 mg BID (twice daily)	Evobrutinib 50 mg BID	Evobrutinib 50 mg BID/Evobrutinib 50 mg BID

(*): Subjects who complete the 52-week Double-blind placebo-controlled period will be offered participation in an optional open label, LTE period for an additional 2 years. During this LTE period, subjects will be administered evobrutinib at an initial dose of 50 mg BID or the eventual Phase III dose, when decided.

All data recorded during the trial will be presented in individual data listings (in the order stated in Table 6). All listings are sorted by treatment group, subject, and time point (where applicable), if not otherwise stated.

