14.6 LTE Efficacy Endpoints

LTE efficacy endpoints will be analyzed on mITT for the LTE Analysis only.

Same methods of imputation used for the PA will be applied to LTE analysis. However, missing efficacy assessments collected after the announcement to the sites of study early termination (i.e. 23 March 2020) will not be imputed.

Table 25 summarizes the analyses that will be performed for each LTE endpoint.

For all LTE efficacy endpoints, the baseline from the 52-weeks treatment period will be used (e.g., SRI responses, change from baseline, etc.).

Institution of EAC-determined protocol-prohibited medication/treatment (i.e., EAC-treatment failure) as well as time to first flare/flare-free/AFR will be censored at the time of announcement to the sites of study early termination (i.e., 23 March 2020).

Table 25: Analysis of LTE endpoints

Endpoint	Method
SRI response over time	
SRI response rate will be summarized over time during LTE period. The baseline from the 52-week treatment period will be used (see Section 9.6).
 
The same analysis will be repeated for subjects with a gap greater than or equal to 2 weeks between 52-week and LTE treatment periods.
 
A line plot representing the SRI response rate over time will be also provided

Low disease activity status over time	Proportions of subjects with LLDAS, SLEDAI-2K \leq 2 or clinical SLEDAI-2K \leq 2 will be summarized over time.
Change over time in CLASI-A and SLICC/ACR Damage Index Score	Descriptive statistics will be presented over time for each endpoint.
Change over time in disease activity as measured by the BILAG, SLEDAI-2K, and PGA	Descriptive statistics will be presented over time for each endpoint.
BICLA response over time	Proportion of subjects with BICLA response will be summarized over time.
Change over time in prednisone-equivalent CS dose	Descriptive statistics will be presented as detailed in Section 14.3.5. This will be applied at LTE Week 24, Week 52 and Week 104.
CCI	

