Time to first flare, flare-free status and annualized flare rate	
Time to first flare, flare-free status and annualized flare rate will be analyzed as in Section 14.3.2 at Week 24, Week 52 and Week 104 with descriptive statistics only. No statistical modeling will be performed.
 
Time to first flare will be assessed starting from randomization (Day 1 of 52-week treatment period) and will be derived for the whole treatment period.
 
Flare analyses will be censored at the time of announcements to the sites of study early termination (i.e. 23 March 2020)

15 Safety Evaluation

For all safety endpoints, data selection for PA and LTE analysis will be handled as indicated in the [Table 26](#).

Table 26 : Data Handling for Safety Analysis

Data summarized	Analysis	Analysis sets	Period covered	Treatment groups

 • AEs • Laboratory data • Vital signs • ECGs • Other safety evaluations 	PA	SAF	All data from 52-week treatment period (safety follow-up included)	
 • Placebo • Evobrutinib 25 mg QD • Evobrutinib 75 mg QD • Evobrutinib 50 mg BID
	LTE analysis	LTE SAF	All data from LTE period (safety follow-up posterior to LTE included)	
 • Placebo/Evobrutinib 50 mg BID • Evobrutinib 25 mg QD/Evobrutinib 50 mg BID • Evobrutinib 75 mg QD/Evobrutinib 50 mg BID • Evobrutinib 50 mg BID/Evobrutinib 50 mg BID

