For the 2 time-to-event figures, a subject reaching the end of study without experiencing the event will have his/her event time right-censored at the time of the last ALT/eGFR assessment or at day 398 (W56 SFU study day + 5) if last assessment is performed after. To be included in a time-to-event figure, a group must have at least one event. Below the horizontal axis of the time-to-event figure, # of subjects at risk will be displayed. The vertical axis may be restricted to 0.50 – 1.0, if none of the curves reach 50%. For LTE time-to-event figures, the starting point will be the Baseline of 52-week treatment period.

In this study, clinically significant lab abnormalities were recorded as adverse events. In lieu of a listing of clinically significant lab abnormalities for each domain, the following by-subject lab value listings will be provided:

- Listing of Grade ≥ 3 hematology values
- Listing of Grade ≥ 3 biochemistry values

- Listing of urinalysis with value ≥ 2 times ULN (excluding values for pH), or an increase of “++” for non-gradable parameters when applicable (for PA only).
- Listing of Grade ≥ 2 AST, ALT or Bilirubin. For each parameter, when a subject has an increase to Grade 2, all posterior values will be included in the listing.

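### LTE flare, ALT and eGFR curves start at randomization or the 52-week Baseline but hold only LTE entrants, so first-year risk may be understated; the ALT/eGFR data and censoring rules also conflict with that origin

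*SAP*

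**What the plan says.** **Population.** SAP Section 8.2.2: "For the LTE analysis, the analysis sets will be drawn from all subjects who enter the LTE". Section 14.6 applies this to efficacy: "LTE efficacy endpoints will be analyzed on mITT for the LTE Analysis only". Table 26 (Section 15) names the LTE SAF for safety. On eligibility, the note to Table 6 in Section 9.2 states: "Subjects who complete the 52-week Double-blind placebo-controlled period will be offered participation in an optional open label, LTE period". Table 7 in Section 10.1 also provides for completers who decline the LTE.

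**Time origin.** For flares, Table 25 in Section 14.6: "Time to first flare will be assessed starting from randomization (Day 1 of 52-week treatment period", derived over the whole treatment period. For the two laboratory time-to-event figures (first ALT grade ≥2, first eGFR below 60), Section 15.3: "For LTE time-to-event figures, the starting point will be the Baseline of 52-week treatment period".

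**Data period and censoring.** Table 26 limits LTE safety data, laboratory data included, to "All data from LTE period (safety follow-up posterior to LTE included". Section 15.3 censors event-free subjects in the two laboratory figures at their last assessment, or at day 398 if that assessment is later, and gives no separate LTE rule. For flares, Table 25 states: "Flare analyses will be censored at the time of announcements to the sites of study early termination (i.e. 23 March 2020". No delayed-entry rule is given for any of these outputs.

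**Status.** Of the LTE flare outputs, Table 25 says: "No statistical modeling will be performed".

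**The concern.** Membership of an LTE set is settled only around Week 52, when a subject has finished the double-blind period and chosen to continue. The curves nevertheless count the preceding 52 weeks as time at risk. A subject who stopped in that year contributes neither the event nor the follow-up to it.

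If the reason for stopping is linked to the event, the first-year part of the LTE curve is selected towards subjects who did well, and every later cumulative estimate carries that shortfall forward. If LTE entry differs by original arm for event-related reasons, comparison of the four treatment sequences is distorted as well. In the Placebo/Evobrutinib sequence the first year is placebo time.

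Section 7 says the reduced LTE analysis focuses on safety, and these are its hepatic and renal time-to-event figures. An LTE curve and a primary-analysis curve over the same first year could disagree with no explanation in the report.

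**Working it through.** The SAP states no flare rate, LTE entry rate or LTE sample size, so there is no figure of its own to reproduce. The structure comes from the text; the arithmetic is illustrative.

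**Step 1: the rules side by side.**
- Section 9.2: entry requires completing 52 weeks. Section 8.2.2: only entrants are analyzed.
- Table 25 and Section 15.3: time runs from randomization or the 52-week Baseline.
- Together, the first 52 weeks are risk time only for subjects known to have completed them.

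**Step 2: direction.** Let F be the true 52-week event risk, and e1 and e0 the probabilities of entering the LTE with and without a first-year event. Then

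P(event by Week 52 | entered) = F·e1 / [F·e1 + (1 − F)·e0].

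If e1 = e0 this equals F, so there is no bias. If e1 < e0 it is below F. Section 14.1.2.1 lists safety (AEs, death) and lack of efficacy among the reasons for stopping treatment, which makes e1 < e0 plausible. It also lists loss to follow-up, withdrawn consent and other reasons, which need not be related to the event.

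**Step 3: illustrative size.** Assumed: e0 = 80%, F = 10–30%, e1 = 0–80%. Example: F = 20%, e1 = 40% gives 0.08 / (0.08 + 0.64) = 11.1%.

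| True F | e1 = 80% | 60% | 40% | 20% | 0% |
|---|---|---|---|---|---|
| 10% | 10.0% | 7.7% | 5.3% | 2.7% | 0% |
| 20% | 20.0% | 15.8% | 11.1% | 5.9% | 0% |
| 30% | 30.0% | 24.3% | 17.6% | 9.7% | 0% |

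The cells show first-year risk as it would appear among LTE entrants.

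**Step 4: the same by Kaplan-Meier.** Simulation of 400,000 subjects per scenario, with exponential flare times, 20% unrelated drop-out by Week 52, and a share q stopping at the first flare. With F = 20%:

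| q | Time | All subjects | LTE entrants only |
|---|---|---|---|
| 0 | Week 52 | 19.9% | 19.9% |
| 50% | Week 24 | 9.9% | 5.5% |
| 50% | Week 52 | 20.0% | 11.1% |
| 50% | Week 104 | 35.8% | 28.7% |

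**Step 5: the ALT and eGFR rules.** 
- *Data period.* If Table 26 is followed, no laboratory value before the LTE counts. With the clock at the 52-week Baseline, year 1 of the curve is then event-free by construction.
- *Censoring day.* Section 15.3 describes day 398 as the Week 56 safety follow-up day plus 5: 56 × 7 + 1 = 393, and 393 + 5 = 398. On the 52-week clock that is 398 − 365 = 33 days after Day 365, so no event-free subject remains at risk beyond about the first month of the LTE. If later events were kept all the same, the remaining risk set would hold only subjects with an event, and the curve could not be interpreted.

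The rule was probably written for the primary analysis, but as worded it covers the LTE figures too.

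**The case against.** **The unselected first-year curves exist elsewhere.** The primary analysis reports time to first severe BILAG A flare and the other flare types on mITT, with discontinuers censored (Sections 14.2.1, 14.2.2.2, 14.3.2). It also reports the ALT and eGFR figures on SAF. This stands, and it limits the harm to readers who take an LTE curve for the all-randomized estimate. Those primary-analysis outputs cover subjects randomized by 28 November 2018.

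**The outputs are descriptive and few.** No test or multiplicity step uses them. The LTE adverse-event tables count LTE-period events only (Section 15.1), so on the safety side just two figures are affected. This stands and sets the weight of the point.

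**The 52-week baseline is a deliberate choice, and the placebo year is disclosed by the group label.** Section 9.6 does adopt that baseline for the LTE. But a reference value for change from baseline is a different matter from a time origin, and choosing the former does not justify the latter in a set defined at Week 52. The label discloses the sequence but not where on the curve placebo time ends.

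**Stronger readings.** A reader might call this immortal time. For flares that is too strong: entrants keep their first-year flares, so the set is conditioned on completion, not on being event-free. A reader might also infer that risk is understated in every group, or that subjects stopped because of raised transaminases. The first depends on how events affect entry. The second is not stated: the SAP gives AEs as a reason for stopping without naming which.

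**Conclusion.** The point holds as a structural flaw in the LTE time-to-event outputs. They use a risk period that precedes, and is conditioned on, membership of the analysis set. First-year risk is expected to be understated if subjects with a flare, ALT elevation or eGFR fall are less likely to enter the LTE, and not at all if entry is unrelated to the event. Its size in this trial cannot be obtained from the SAP; every percentage in the illustration rests on assumed risks and entry probabilities.

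The ALT and eGFR figures have a further defect that needs no assumption: the origin, the data period in Table 26 and the day-398 rule cannot all be applied to give a usable LTE curve.

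The change should be made, but nothing in the primary analysis or the hypothesis tests depends on it.

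**What to change.** Choose one of two consistent definitions and state it in Table 25, Table 26 and Section 15.3.

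1. **LTE sets, LTE clock.** Start time at the first LTE dose, already defined in Section 9.7, and set an LTE-specific censoring day for the ALT and eGFR figures. Table 26 can then stay as it is. State how subjects whose event had already occurred before LTE Day 1 are handled. The downside is that the output no longer describes time to first flare over the whole treatment period; the primary analysis already reports the first year for its cohort.
2. **Origin kept at randomization or Baseline.** Include all randomized mITT subjects (flare) or SAF subjects (ALT, eGFR), not limited to the primary-analysis cut-off, with non-entrants censored at the end of their own follow-up. Amend Table 26 so that 52-week laboratory data enter these figures, replace the day-398 limit, and mark the placebo period in the Placebo/Evobrutinib group. This still assumes that censoring at discontinuation is uninformative.

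Either option costs SAP wording plus a changed start date or population flag, and requires no new data.

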15.1 Adverse Events

All analyses described in this section will be based on treatment-emergent adverse events (TEAEs) if not otherwise specified.

For the PA, TEAEs will be defined as:

- AEs starting on or after first treatment administration of any IMP (placebo or evobrutinib) until safety follow up (end of study) or first administration in LTE for subjects continuing in LTE,
- or if it was present prior to any IMP administration but exacerbated after.

Any AE which started before study first treatment administration of any IMP (placebo or evobrutinib) but improved during treatment period until safety follow up (end of study) or first administration in LTE for subjects continuing in LTE will not be counted as TEAE.

For the LTE analysis:

- For subjects who enter the LTE, TEAEs will be defined as:
 - AEs starting on or after first treatment administration of evobrutinib 50 mg BID during LTE until the end of study.
 - AEs starting prior first treatment administration of evobrutinib 50 mg BID during LTE, but exacerbated during the LTE

Only AEs from LTE period will be considered including AEs during the LTE safety follow-up period. Any AE which started before study first treatment administration of evobrutinib 50 mg BID but improved during LTE period will not be counted as TEAE.

Incomplete AE-related dates will be handled as follows:

- In case the onset date is missing completely or missing partially but the onset month and year, or the onset year are equal to the start of IMP then the onset date will be replaced by the minimum of start of IMP and AE resolution date.
- In all other cases the missing onset day or missing onset month will be replaced by 1.
- Incomplete stop dates will be replaced by the last day of the month (if day is missing only), if not resulting in a date later than the date of subject's death. In the latter case, the date of death will be used to impute the incomplete stop date.

Further information collected after the cut-off for an analysis (such as a fatal outcome) may be extracted from the Safety data base and presented separately in the CSR.

15.1.1 All Adverse Events

AEs will be coded according to the latest MedDRA version available at the time of analysis. The severity of AEs will be graded using NCI-CTCAE version 4.03 toxicity grades. AEs with missing classification concerning IMP relationship will be considered related to the IMP.

15.1.1.1 3-Tier Approach

The 3-tier approach is a systematic way to summarize and analyze adverse events (AEs) in clinical trials (Crowe 2009). AEs in different tiers are analyzed using different levels of statistical analyses.

3-Tier approach will be used for PA only.

The AEs identified by the Benefit Risk Action Team for Tier 1 reporting in this trial are in [Table 27](#).

Table 27: Tier 1 AEs

Tier 1 AE (PT)	Within group summary	Between group comparison (Evobrutinib - Placebo) 95% CI
Transaminases elevations Alanine aminotransferase abnormal Alanine aminotransferase increased Aspartate aminotransferase abnormal Aspartate aminotransferase increased Hypertransaminasaemia Transaminases abnormal Transaminases increased	n (%)	Δ [xx%, xx%]

Tier 1 AE will be identified using sponsor-defined list of search term as defined in [Table 27](#) (refer to Appendix 18.14).

All AEs will be further classified into Tier 2 or Tier 3 based on the Rule-of-3. If there are 3 or more subjects with the reported term in any treatment group, that term will be included in Tier 2. Otherwise, it will be included in Tier 3.

The Tier 1 and Tier 2 AEs will be assessed with a 95% CI for between-group comparisons. For the difference in crude rates, the CIs will be based on MN method ([Miettinen 1985](#)).

Exposure Adjusted Incidence Rate (EAIR) of TEAEs will also be separately presented for each Tier, by SOC and PT (see Section 15.1.1.3 for multiple events handling). For this trial, difference in EAIR will also be summarized. For Tier 1 and Tier 2 AEs, the CIs will be calculated using a Poisson binomial model. An example of SAS code is available in Appendix 18.9.

No multiplicity adjustment will be applied for Tier 1 and 2 AEs. The Tier 3 AEs will be assessed via summary statistics and risk differences.

For each comparison of evobrutinib group with placebo, forest trees for Tier 1 and Tier 2 AEs will be provided as well, displaying the incidence rate and associated 95% CI of difference.

15.1.1.2 Overview of TEAEs

Two summary tables of TEAEs will be provided as described in [Table 28](#).

Table 28: Summary Tables of TEAEs

Summary	Modalities

Overview of TEAEs
	
 • Any TEAE • IMP related TEAE • Serious TEAE • IMP related serious TEAE • TEAE with NCI-CTCAE grade 1 • IMP related TEAE with NCI-CTCAE grade 1 • TEAE with NCI-CTCAE grade 2 • IMP related TEAE with NCI-CTCAE grade 2 • TEAE with NCI-CTCAE grade 3 • IMP related TEAE with NCI-CTCAE grade 3 • TEAE with NCI-CTCAE grade 4 • IMP related TEAE with NCI-CTCAE grade 4 • TEAE leading to death • IMP related TEAE leading to death

Overview of TEAEs leading to Actions:
 
 • Change in dose, • Administration of medication, • Procedure, • Study termination 	
 • TEAE with no change of dose • IMP related TEAE with no change of dose • TEAE leading to dose reduction • IMP related TEAE leading to dose reduction • TEAE leading to dose increase • IMP related TEAE leading to dose increase • TEAE leading to interruption of IMP • IMP related TEAE leading to interruption of IMP • TEAE leading to withdrawal of IMP • IMP related TEAE leading to withdrawal of IMP • TEAE leading to administration of concomitant medication • IMP related TEAE leading to administration of concomitant medication • TEAE leading to concomitant procedure • IMP related TEAE leading to concomitant procedure • TEAE leading to study termination • IMP related TEAE leading to study termination

15.1.1.3 Tabulation of Adverse Events by SOC and PT

The TEAE tables to be prepared are listed in [Table 29](#).

Table 29: TEAE Tables to be produced

	Overall frequency	By primary SOC and PT	By PT only	By primary SOC, PT and worst grade	PA	LTE analysis	HDA subpopulation analysis for PA
TEAE overview summary	✓	NA	NA	NA	✓	✓	✓
TEAE leading to discontinuation of IMP/study/dose reduction of IMP overview summary	✓	NA	NA	NA	✓	✓	✓
All TEAEs	✓	✓	✓	✓	✓	✓	✓
Serious TEAEs	✓	✓			✓	✓	✓
Non-serious TEAEs*	✓	✓			✓	✓	✓
TEAEs leading to IMP withdrawal	✓	✓			✓	✓	✓
TEAEs leading to study termination	✓	✓			✓	✓	✓
TEAEs leading to death	✓	✓			✓	✓	✓
IMP-related TEAEs	✓	✓	✓	✓	✓	✓	✓
IMP-related serious TEAEs	✓	✓			✓	✓	✓
IMP-related TEAEs leading to IMP withdrawal	✓	✓			✓	✓	✓
IMP-related TEAE leading to study termination	✓	✓			✓	✓	✓
IMP-related TEAEs leading to death	✓	✓			✓	✓	✓
EAIR	✓	✓			✓	✓	✓

(*): A table with all non-serious TEAEs will be first provided and then only TEAEs exceeding a frequency of 5% in at least one of the treatment groups (> 5%), by SOC and PT will be provided.

Specific rules for SOC/PT tabulation

All AEs recorded during the trial (i.e., assessed from signature of informed consent until the end of the Follow-up/End of Trial visit) will be coded according to the MedDRA and assigned to a SOC and PT.

SOC terms will be sorted alphabetically.

- For the PA, each treatment group as well as evobrutinib combined (25 mg QD, 75 mg QD and 50 mg BID) will be computed and displayed in the table. PTs within each SOC will be sorted by descending frequency of this evobrutinib combined, and then alphabetically if multiple PTs have the same frequency.
- For the LTE analysis, PTs within each SOC will be sorted by descending frequency in the highest dose of evobrutinib (i.e., subjects who are administered evobrutinib 50 mg BID throughout the study), and then alphabetically if multiple PTs have the same frequency.

If a subject experiences more than one occurrence of the same TEAE (same SOC and same PT) during the trial, the subject will be counted only once for that treatment (the worst severity and the worst relationship to trial treatment will be tabulated).

In case a subject had events with missing and non-missing grades, the maximum of the non-missing grades will be displayed.

EAIR are calculated as number of subjects with AE divided by the sum of the individual times of all subjects in the safety population from start of treatment to first onset of AE. If a subject has multiple events, the exposure period of the first event is used. For a subject with no event, the exposure period is censored at the last follow-up time for the AE summarization period. The incidence rate multiplied with 1000 would give the number of AEs expected in 1000 subjects within 1-time unit (for example 1 year). EAIR of TEAEs will be presented by SOC and PT.

Subject data listings

TEAEs and non-TEAEs (i.e. pre-treatment AEs) will be listed separately by treatment group and subject. For subjects with a gap greater than or equal to 2 weeks between 52-Week treatment period and LTE treatment period, AEs collected during the gap period will be presented in specific data listings.

A listing of TEAEs leading to withdrawal of IMP, a listing of TEAEs leading to study termination, if any, will be provided as well.

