If the System Organ Class (SOC) or Anatomical Therapeutic Class (ATC) term is missing/not coded yet, then ‘Uncoded SOC’ (or ‘Uncoded ATC’) will be indicated at the TLF level. When a Preferred Term (PT) is missing, it will be set to ‘Uncoded PT: verbatim text’.

Treatment day:

Treatment day is defined as relative day to the start date of treatment. Treatment day will be calculated as the number of days since the first administration of any IMP. The day before is defined as Treatment day –1 (no Treatment day 0 is defined). Treatment day will only be presented in subject safety data listings.

For the 52-week treatment period, start date of treatment is defined as the date of first administration of randomized study drug.

For the LTE treatment period, start date of treatment is defined as the date of first treatment administration on or after the date of end of 52-week treatment.

On-Treatment flag:

On-treatment values are results of assessments done from the first IMP administration on Day 1 till End of Study (completion or early termination).

Repeated and unscheduled measurements:

Repeated and unscheduled measurements are included in the listings. Data collected at both unscheduled and scheduled visits will be used for shift tables. For summary statistics, figures, or inferential analysis, data are re-allocated to an analysis visit using time window calculations (see below).

Gap between 52-Week treatment period and LTE treatment period:

Subjects with a gap greater than or equal to 2 weeks between 52-Week treatment period and LTE period will be analyzed the same way as subjects without a gap. The gap will be defined using the last dose received during the 52-week treatment period and the first dose received during the LTE treatment period. Specific data listings on safety data (AEs and laboratory data) collected during the gap period will be produced for these subjects for the LTE analysis. In addition, for the subgroup of subjects with a gap greater than or equal to 2 weeks, the following analyses will be provided:

- Summary statistics of the gap duration
- SLE disease baseline characteristics at LTE Day 1
- SRI-4 response and SRI-6 response among HDA subjects by LTE visit

Time windows:

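### EAIR time is counted to AE onset, which gives negative person-time for pre-existing AEs that worsen and keep their original onset date; the effect is negligible in the PA and possibly several percent in the descriptive LTE tables

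*SAP*

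**What the plan says.** **Rate.** SAP Section 15.1.1.3 defines EAIR as the number of subjects with the AE divided by "the sum of the individual times of all subjects in the safety population from start of treatment to first onset of AE". When there are several events, "If a subject has multiple events, the exposure period of the first event is used". Subjects without an event are censored at their last follow-up in the summarised period. The rate applies to treatment-emergent events: "EAIR of TEAEs will be presented by SOC and PT". Table 29 orders it overall and by SOC and PT, for the PA, the LTE analysis and the HDA subpopulation.

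**Events.** Section 15.1 defines TEAEs by onset on or after first dose, and adds a second route for pre-existing events. For the PA an AE also qualifies "or if it was present prior to any IMP administration but exacerbated after". For the LTE the second route is "AEs starting prior first treatment administration of evobrutinib 50 mg BID during LTE, but exacerbated during the LTE".

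**Start of treatment.** Section 9.7, under Treatment day, gives one date per period. For the 52-week period, "start date of treatment is defined as the date of first administration of randomized study drug". For the LTE, "start date of treatment is defined as the date of first treatment administration on or after the date of end of 52-week treatment".

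The SAP has no rule that replaces the onset of a worsened AE by its date of worsening, and none that sets a minimum time. The onset-date imputation in Section 15.1 deals only with missing or partial dates.

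**The concern.** The numerator and the denominator do not fit together. A TEAE that qualifies by exacerbation has, by definition, an onset before the start of the period. Start of treatment to onset is then a negative interval, and the subject still counts as a case. The direction of the error is fixed: each such subject shrinks the person-time and raises the rate.

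The exposure to this error differs by period. In the PA the onset can only fall between consent, when AE collection begins, and Day 1. In the LTE it can fall anywhere in the preceding 52 weeks of double-blind treatment. Section 7 of the SAP reduces the LTE analysis to a focus on safety, so the AE tables are a main product of that period. The rows most exposed are the overall row and the large SOCs, where many subjects have an event and the total time to first event is short.

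**Working it through.** The SAP states no EAIR and no AE counts, so there is no figure to reproduce. All counts and times below are assumptions, apart from the PA group size, which is 469/4 ≈ 117 from Section 8.2.2.

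**One subject.** Let the LTE start on day 366 of the study.
- AE onset on day 30, worsening in the LTE: (30 − 366)/365.25 = −0.92 year.
- AE onset on day 300: (300 − 366)/365.25 = −0.18 year.

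**LTE, any TEAE.** EAIR = 1000 × subjects with TEAE / sum of times. Assume 80 subjects: 56 with a TEAE at a mean of 0.25 year, and 24 without, followed 0.9 year. Event-free time is 24 × 0.9 = 21.6 years. Let *k* of the 56 have an AE carried over with onset on average 0.5 year before the LTE start.

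| Time given to the *k* subjects | *k* = 3: person-years | EAIR per 1000 | *k* = 6: person-years | EAIR per 1000 |
|---|---|---|---|---|
| As written (−0.5 year) | 53 × 0.25 + 21.6 − 1.5 = 33.35 | 1679 | 50 × 0.25 + 21.6 − 3.0 = 31.1 | 1801 |
| 1-day floor | 53 × 0.25 + 21.6 + 3/365.25 = 34.86 | 1606 | 50 × 0.25 + 21.6 + 6/365.25 = 34.12 | 1641 |
| Worsening at 0.25 year | 56 × 0.25 + 21.6 = 35.6 | 1573 | 35.6 | 1573 |

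The excess of the rule as written over the 1-day floor is 34.86/33.35 − 1 = 4.5% for *k* = 3 and 34.12/31.1 − 1 = 9.7% for *k* = 6. Against a known worsening date at 0.25 year it would be about 7% and 14%.

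**LTE, narrower rows.** Assume 80 subjects, 1 year of follow-up, and compare with a floor at 0.
- Rare PT, 4 events, 1 carried over at −0.5 year: 76 + 3 × 0.5 = 77.5 years with the floor and 77.0 as written. The rates are 51.6 and 51.9 (+0.6%).
- Rare PT, 4 events, 2 carried over at −0.9 year: 77.0 and 75.2 years; 51.9 and 53.2 (+2.4%).
- Common SOC, 30 events, 3 carried over at −0.5 year: 50 + 27 × 0.35 = 59.45 and 57.95 years; 504.6 and 517.7 (+2.6%).
- Common SOC, 30 events, 6 carried over at −0.5 year: 50 + 24 × 0.35 = 58.4 and 55.4 years; 513.7 and 541.5 (+5.4%).

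**PA, any TEAE.** Assume 117 subjects, 90 with a TEAE, of whom 5 had onset 14 to 28 days before Day 1; the other 85 have events at 0.2 year and the 27 without are followed 1 year.
- Floor at 0: 85 × 0.2 + 27 = 44.0 years, rate 2045.5.
- As written: 44.0 − 5 × 14/365.25 = 43.81 years (2054), or 44.0 − 5 × 28/365.25 = 43.62 years (2063).
- Excess from negative time: +0.4% to +0.9%. Against a worsening date at 0.2 year (45.0 years, rate 2000) it is +2.7% to +3.2%. Most of that gap comes from placing the event at the start rather than at its worsening.

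**The case against.** **The problem may not arise in the data.** If the eCRF enters a worsening as a new AE with its own onset date, no time is negative. AE recording rules normally sit in the protocol and eCRF instructions, which are not at hand. This stands, and it is why the point is conditional. The SAP does not state such a convention, and its TEAE wording about AEs that start earlier and are later exacerbated suits a single record that keeps its onset.

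**The SAP limits the LTE to LTE data.** Section 15.1 says that only AEs of the LTE period are considered, Table 26 says the same of the data, and Section 15.1.1.3 speaks of an exposure period, which nobody would intend to be negative. But the restriction does not cancel the bullet that expressly admits worsened earlier AEs, and it supplies no date for them.

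**The LTE start date in Section 9.7 was not written for EAIR.** That definition serves Treatment day, which appears only in listings, and Section 15.3 starts the LTE laboratory time-to-event figures at the 52-week Baseline. This is fair. The first LTE dose is the natural origin for an LTE rate, but the SAP should say so. Starting from Day 1 of the 52-week period would avoid most negative times at the price of putting about a year of pre-LTE time in the denominator.

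**No planned comparison is harmed in the LTE.** A reader might infer that comparisons across the former arms are distorted. The documents do not support that. Differences in EAIR and their confidence intervals belong to the 3-tier approach, which Section 15.1.1.1 restricts to the PA. The LTE EAIR is a descriptive table by former arm, with all groups on the same LTE regimen in Table 6.

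**Conclusion.** The point holds in conditional form. Where a worsened pre-existing AE keeps its original onset date, the stated rule yields negative person-time and an overstated rate, and nothing else in the SAP corrects it.

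In the PA, negative time adds under 1% on assumed inputs, so the planned EAIR differences are not materially affected. In the LTE the overall row could be about 5% to 10% too high against a 1-day floor, large SOC rows a few percent, and rare PTs up to about 2%. All of this rests on assumed group sizes, event counts, times and numbers of carried-over AEs.

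Two stronger readings go too far. One is that inflated LTE rates are a certainty; that depends on AE recording rules that the SAP does not give. The other is to take 7% to 14% as the size. That range presumes that every affected subject's worsening is dated, at an average of 0.25 year into the LTE, and the SAP mentions no such date.

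**What to change.** Add to Section 15.1.1.3, for both the PA and the LTE analysis:

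- Start of treatment for EAIR is the first dose of the period analysed.
- For a TEAE that qualifies by exacerbation, the event date is the date of worsening if recorded, and otherwise the first dose date of the period.
- Event time is event date minus first dose date plus 1, and no subject contributes less than 1 day.

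If a worsening is in fact recorded as a new AE, say so in the same place; the floor then does no harm.

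The cost is two or three sentences and one line in the AE time derivation. Nothing further has to be collected, because the fallback covers an unrecorded worsening date. The downside is that the 1-day convention slightly understates person-time. In the LTE example, if the true worsening were at 0.25 year, the rate would be 1606 (3 subjects) or 1641 (6 subjects) rather than 1573, that is about 2% or 4% too high. That is still closer than the rule as written.
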